1.2 Protocol Administrative Information

Protocol Number: OCM-OAS-01

Revision Number: Version 3.0

Protocol Date: 07-Sep-2022

Investigational Product: OrthoCor Active System

1.3 Amendment History:

Date	Amendment Number	Amendment Type
30-Nov-2021	Original	Original protocol, version 1.0
18-Jan-2022	1	Amended protocol, version 2.0
07-Sep-2022	2	Amended protocol, version 3.0

2.0 PROTOCOL SYNOPSIS

Sponsor	Caerus Corporation
Protocol Title:	Prospective, Multi-Center, Randomized Study to Evaluate the OrthoCor Active System for Pain Relief
Protocol Number	OCM-OAS-01
Investigational Device:	OrthoCor Active System
Device Description:	The OrthoCor Active System is a portable (battery operated) non-invasive device that delivers Pulsed Electromagnetic Field (PEMF) therapy for General Use of temporary pain relief, utilizing wraps that position the therapy, such as on the ankle, back, knee, wrist, elbow, shoulder, foot, or neck. The microchip delivers the pulsed RF signal to the tissue target via the inductive coupling with an applicator coil. The system also uses disposable, single-use, air activated OrthoPods that provide heat.
Study Objective:	The objective of this study is to evaluate the OrthoCor Active System in individuals prescribed its use in comparison with Standard of Care (SOC) intervention. Pain assessments will be conducted utilizing the Mankoski Pain Scale.
Study Design:	Prospective, Multi-Center, Randomized, Open Label Study.
Subject Population:	Both males and females, presenting to the designated study sites with pain in superficial soft tissue, such as in the ankle, back, knee, wrist, elbow, shoulder, foot, or neck who are prescribed the use of the OrthoCor Active System or Standard of Care (SOC) intervention.
Rationale:	
According to the Centers for Disease Control and Prevention, 50 million adults in the United States have chronic daily pain, with 19.6 million adults experiencing high impact chronic pain that interferes with daily life or work activities.
 
Clinical best practices may recommend a collaborative, multimodal, multidisciplinary, patient-centered approach to treatment for various acute and chronic pain conditions to achieve optimal patient outcomes. For improved functionality, activities of daily living, and quality of life, clinicians are encouraged to consider and prioritize, when clinically indicated, nonpharmacologic approaches to pain management.
 
An alternative treatment option can be the use of restorative therapies. Restorative therapies play a significant role in acute and chronic pain management, and positive clinical outcomes are more likely if restorative therapy is part of a multidisciplinary treatment plan following a comprehensive assessment. Patient outcomes related to restorative and physical therapies tend to emphasize

	
improvement in outcomes, but there is value in restorative therapies to help maintain functionality.
 
The Orthocor Active System delivers OrthoCor's patented Pulsed Electromagnetic Field (PEMF) therapy, a noninvasive, temporary relief for pain. The key to OrthoCor's therapy is the use of specialized PEMF technology. In particular, PEMF works at the source of injuries, and helps accelerate the body's natural anti-inflammatory and recovery responses. Inside every Active System is the OrthoCor, a microchip that delivers PEMF directly to the source of injuries. Furthermore, PEMF has been shown to stimulate reaction pathways that result in pain and inflammation reduction.

Study Assessment/ Evaluation:	Pain assessments will be conducted utilizing the Mankoski Pain Scale which will be compared to the pain assessments of subjects who were prescribed the Standard of Care (SOC) intervention.
Study Endpoints:	
Primary Safety Endpoint: The safety endpoint of this study will be the adverse events reported with the OrthoCor Active System pain after 2 weeks of use.
 
Primary Efficacy Endpoint: The efficacy endpoint of this study will be the comparison of the OrthoCor Active System pain assessment scores to the Standard of Care (SOC) intervention after 2 weeks of use.

Exploratory Assessment:	
Exploratory Assessment: The exploratory assessment of this study will be the performance of the OrthoCor Active System after an additional 2 weeks of use and is intended for research and publication only.

Number of Patients:	
Up to 100 subjects will be enrolled in order to achieve up to 50 using the OrthoCor Active System and up to 50 using the Standard of Care (SOC) intervention. The patients will be enrolled consecutively at the participant site until enrollment is met.
 
For the exploratory assessments, the 50 subjects who received SOC will have the opportunity to cross-over and use the OrthoCor Active system.

Number of Sites:	Five (5) sites are anticipated
Anticipated Study Duration:	3-5 months
Study Eligibility Criteria	
Inclusion Criteria:
 
Participants must meet ALL of the following:
 
 1. Individuals presenting with pain in superficial soft tissue, such as ankle, back, knee, wrist, elbow, shoulder, foot, or neck pain,

	
or minor muscular and joint aches and pains associated with over exertion, strains, sprains, or arthritis
 
 2. Prescribed use of the OrthoCor Active System or Standard of Care (SOC) intervention 3. Willing and able to provide informed consent or obtain consent from legal authorized representative (LAR) 
Exclusion Criteria:
 
Participants must not meet ANY of the following:
 
 1. Have a cardiac pacemaker, cardioverter defibrillator, neurostimulator, infusion pump or any active medical implant 2. Have an implanted metallic lead or any type of wire coil implant, or any implanted system that may contain lead 3. Current or expected use of opioids 4. Who are or may be pregnant 5. Have an open wound at the area of application 6. Are not capable or fully aware to the sensation of heat 7. Have poor circulation or heart disease 8. Have diabetes 9. Under the age of 18 or individuals with open bone growth plates 10. Unable to provide consent or obtain consent from a LAR 11. Unwilling or unable to use the OrthoCor Active System or Standard of Care (SOC) intervention 12. Unwilling or unable to complete the daily pain assessment 13. Enrolled in a study to evaluate an investigational drug 14. Prisoner or under incarceration
Statistical Analysis	
Primary efficacy analyses
 
The primary effectiveness endpoint of this study is the change from baseline of the OrthoCor Active System compared to the Standard of Care (SOC) intervention.

3.0 LIST OF ABBREVIATIONS

Abbreviation	Definitions
AE	Adverse Event
CFR	Code of Federal Regulations
CIOMS	Council for International Organizations, Medical Sciences
CRF / eCRF	Case Report Form/ Electronic Case Report Form
CRO	Contract Research Organization
EDC	Electronic Data Capture
eDiary	Electronic Diary
FDA	Food and Drug Administration
GCP	Good Clinical Practice
HIPAA	Health Insurance Portability and Accountability Act
ICF	Informed Consent Form
ICH	International Council for Harmonisation
IFU	Instructions For Use
IRB	Institutional Review Board
LAR	Legal Authorized Representative
PD	Protocol Deviation
PEMF	Pulsed Electromagnetic Field
PI	Principal Investigator
POC	Point of Care
RF	Radio Frequency
SAE	Serious Adverse Event
SADE	Serious Adverse Device Effect
SD	Standard Deviation
SDV	Source Data Verification
SID	Subject Identification Number
SOC	Standard of Care
UADE	Unanticipated Adverse Device Effect
WOCBP	Women of Child Bearing Potential

4.0 INTRODUCTION

4.1. Background and Significance

According to the Centers for Disease Control and Prevention, 50 million adults in the United States have chronic daily pain, with 19.6 million adults experiencing high impact chronic pain that interferes with daily life or work activities. Clinical best practices may recommend a collaborative, multimodal, multidisciplinary, patient-centered approach to treatment for various acute and chronic pain conditions to achieve optimal patient outcomes. For improved functionality, activities of daily living, and quality of life, clinicians are encouraged to consider and prioritize, when clinically indicated, nonpharmacologic approaches to pain management.¹

An alternative treatment option can be the use of restorative therapies. Restorative therapies play a significant role in acute and chronic pain management, and positive clinical outcomes are more likely if restorative therapy is part of a multidisciplinary treatment plan following a comprehensive assessment.¹

The OrthoCor Active System uses specialized Pulsed Electromagnetic Field (PEMF) technology to relieve pain and reduce edema through safe, clinically proven therapy. PEMF is a low-level, time-varying electromagnetic field that penetrates superficial soft tissue, helping to accelerate the body's natural anti-inflammatory and recovery responses. Inside every OrthoCor Active System is proprietary electronic circuitry that delivers PEMF to the source of injuries. PEMF has been shown to stimulate reaction pathways that result in pain and inflammation reduction. OrthoCor's patented PEMF accelerates the binding of calcium (Ca²⁺) to calmodulin (CaM), the process responsible for the body's natural, anti-inflammatory nitric oxide (NO) cascade²⁻⁵. NO is a key element in the body's natural healing process. It is also a vasodilator, increasing blood and lymphatic flow.³ Additionally, NO down-regulates interleukin-1 beta (IL1 β) and inducible nitric oxide synthase (iNOS), which leads to reduced cyclooxygenase-2 (COX-2) and prostaglandins – molecules responsible for causing inflammation and pain²⁻⁵. Unlike other systemic COX-2 inhibitors such as nonsteroidal anti-inflammatory drugs (NSAIDs), OrthoCor's targeted PEMF signals stimulate localized reaction pathways, thereby reducing pain and inflammation without the risks and side effects associated with NSAIDs²⁻⁵.

4.2. Previous Experience

In previous clinical studies, OrthoCor Active System was clinically proven to reduce pain, swelling and provide lasting relief without the use of pain medications or invasive procedures.

OrthoCor Medical Inc. conducted a prospective, double blind, placebo controlled, randomized pilot study (2014-2016), enrolling 80 patients with Kellgren-Lawrence knee arthritis who used the OrthoCor knee system, which showed a significant 60% reduction in the mean pain score within the first 3 days of use compared with the sham group².

[figure not shown]

Fig. 3 Effect of a radio frequency PEMF signal, configured, a priori, to target the CaM/NO/cGMP signaling pathway, on pain from early stage knee OA. This is a repeated measures intra-cohort comparison which shows this signal caused a nearly 60 % reduction in mean VAS pain scores within the first 3 days for the active cohort, which persisted to day 42 for all enrolled active patients. There was no significant difference in mean VAS scores for the sham cohort at any time point, or in mean baseline VAS scores for the active and sham cohorts

A preliminary study⁶ conducted by OrthoCor Medical Inc. in 33 patients suffering from knee osteoarthritis utilizing the OrthoCor knee system, showed reduced pain and stiffness after 15 days of treatment with a 43% reduction in pain score (Figure 3) and a 79% improvement in activity limitations, symptoms, emotions, and overall quality of life (Figure 2).

[figure not shown]

Figure 2. Average score for level of improvement portion of PGIC questionnaire. The results show a 79% improvement in development after 15 days of therapy.

[figure not shown]

Figure 3. Average score for pain level portion of PGIC questionnaire. A score of 10 indicates a maximum increase in pain. The results show that pain level has decreased 43% following 15 days of therapy.

4.3. Name and Intended Use

The OrthoCor Active System is a portable (battery operated) non-invasive shortwave diathermy medical device which applies electromagnetic energy at a radio frequency (RF) of 27.12 MHz for the treatment of pain in superficial soft tissue, such as in the ankle, back, knee, wrist, elbow, shoulder, foot, or neck. The OrthoCor Active System delivers the pulsed RF signal of $6.5+0.5$ Ws/cm³ to the tissue target via the inductive coupling with an applicator coil. The system also uses disposable, single-use, air activated OrthoPods that provide heat for the temporary relief of minor muscular & joint aches & pains associated with over-exertion, strains, sprains, and arthritis.

4.4. Indication for Use

The OrthoCor Active System is indicated for adjunctive use in the treatment of pain, and temporary relief of minor muscular and joint aches and pains associated with over-exertion, strains, sprains, and arthritis.

5.0 STUDY RATIONALE

The objective of this study is to evaluate the OrthoCor Active System in individuals presenting with post-operative pain and edema in superficial soft tissue. The OrthoCor Active System will be compared to the SOC intervention.

6.0 DEVICE DESCRIPTION

The OrthoCor Active System includes the following components:

Multi-Use

- The Active System can be used in multiple body locations, some examples are shown below

Figure 1. OrthoCor Active System Multi-Use (Not to scale).

The OrthoCor Active system has PEMF and heat as the active components as provided by the 2 OrthoPods inserted in the body specific wraps for the purpose of holding them in place.

The OrthoPods are the same for all body location configurations and only the wrap is modified for the purpose of holding them in the treated area.

Figure 2. Image shows the Use of OrthoCor Active Ankle System (Not to scale).

Figure 3. Image shows the Use of OrthoCor Active Back System (Not to scale).

Figure 4. Image shows the Use of OrthoCor Active Knee System (Not to scale).

Figure 5. Image shows the Use of OrthoCor Active Wrist System (Not to scale).

Figure 6. Image shows the Use of OrthoCor Active Elbow System (Not to scale).

Figure 7. Image shows the Use of OrthoCor Active Shoulder System (Not to scale).

Figure 8. Image shows the Use of OrthoCor Active Neck System (Not to scale).

Single-Use

- OrthoPods

Instructions for Use manual is provided to the patient with the product (see Appendix A).

7.0 STUDY OBJECTIVES and ENDPOINTS

The primary objectives are to compare the pain assessment scores of the SOC intervention to the OrthoCor Active System pain assessment scores.

The primary effectiveness endpoint of this study is the change from baseline of the OrthoCor Active System compared to the SOC intervention.

8.0 STUDY DESIGN

8.1 Study Details

This is a prospective, multi-center, randomized, open label study that will enroll up to 100 subjects.

8.2 Number of Clinical Sites

The trial will be conducted in up to five (5) participating sites in the USA.

8.3 Subject Population

The target population for this measurement consists of both males and females, presenting to the designated study sites with pain in superficial soft tissue, such as in the ankle, back, knee, wrist, elbow, shoulder, foot, or neck who are prescribed the use of the OrthoCor Active System or Standard of Care (SOC) intervention.

Eligible subjects must meet the inclusion and exclusion criteria described in Sections 8.4 and 8.5. Any questions from the investigative site regarding a potential subject's eligibility for enrollment must be discussed with the Sponsor (or designee) prior to consenting and enrolling the subject into the study for the investigational measurement.

It is estimated that up to 100 subjects may be enrolled into the study.

Patients will be enrolled consecutively at each participant site until up to 50 using the OrthoCor Active System and up to 50 using the Standard of Care (SOC) intervention have enrolled. The CRO will stratify the arms (OrthoCor Active System vs SOC) by selecting the arm alternatively. The patients will be enrolled consecutively at the participant site until enrollment is met.

As part of exploratory research extension, patients using the OrthoCor Active system will have the opportunity to continue on the trial for an additional 2 weeks. Participants assigned SOC have the opportunity to cross-over using the OrthoCor Active system for the additional 2 weeks. Participation in the exploratory extension is optional.

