9.3 Baseline/Enrollment and Study Evaluations

A study specific Subject Identification Number (SID) will be assigned in consecutive order after informed consent is obtained.

The following data will be collected:

- Patient demographics (at minimum Gender, Age and Race)
- Surgical Date
- Patient Pain Assessment
- Patient self-reported pre-existing conditions (list, if confirmed), if available
- OrthoCor Active System or SOC intervention use details
- Device information (serial number on OrthoCor Active System and OrthoPods)
- Concomitant Pain Medication Use
- Pregnancy Test Results

For those subjects that elect to participate in the research exploratory extension, the patient pain assessment will be collected for another 2 weeks. The extension data will be used for research and publication only.

OrthoCor Active System: Subject(s) are to apply a fully charged brace with a new set of OrthoPods over the affected area for a total of 2 hours at their first convenient opportunity each day. Subject(s) should be instructed to contact the site if they experience unusual sensations or discomfort during the use of the brace.

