11.3. Timing of Analyses

The final analysis will be performed after all enrolled participants have completed the 2 weeks treatment period.

The additional analysis for exploratory research will be performed after all enrolled participants completed the 2 weeks of treatment and any of the additional exploratory days and up to 2 weeks.

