12.2. Exploratory Endpoints

The exploratory endpoints of this study will be to compare the reduction of pain symptoms from baseline on the Mankoski Pain Scale after 4 weeks of treatment with the OrthoCor Active System device and Standard of Care.

Usage (device records use), feedback via participant diaries, usability assessment, user preferences will be summarized as descriptive statistics.

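### The 4-week exploratory result rests on subjects who chose to continue, and the plan neither defines its analysis set nor guards against selection bias of unknown direction

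*Protocol*

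**What the plan says.** - **Who continues.** Protocol 8.3: "Participation in the exploratory extension is optional". The same section says of the other arm: "Participants assigned SOC have the opportunity to cross-over using the OrthoCor Active system for the additional 2 weeks".
- **Who supplies data.** Protocol 9.3: "For those subjects that elect to participate in the research exploratory extension, the patient pain assessment will be collected for another 2 weeks". No collection after Day 14 is described for anyone else.
- **What is estimated.** SAP 12.2 sets out to "compare the reduction of pain symptoms from baseline on the Mankoski Pain Scale after 4 weeks of treatment" with the device and with standard of care (SOC). The synopsis describes the exploratory assessment as the "performance of the OrthoCor Active System after an additional 2 weeks of use".
- **Which data enter.** SAP 11.3 runs the exploratory analysis once subjects have finished the 2 weeks and "any of the additional exploratory days and up to 2 weeks".
- **Method and missing data.** SAP 12 names repeated-measures ANOVA. SAP 12.4 gives a complete-case rule, then says that carrying the last visit forward may be considered. SAP 11.2 runs efficacy analyses on both the ITT and per-protocol populations. SAP 12.6 attaches the complete-case rule to the per-protocol analysis and puts all subjects in the ITT analysis.
- **Blinding and purpose.** SAP 9 says there is none. Protocol 9.3 limits the use of the extension: "The extension data will be used for research and publication only".

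**The concern.** Each subject records a pain rating daily and knows the assigned treatment. By Day 14 each therefore knows how the pain has gone and decides on continuation with that knowledge. If the decision is related to improvement, the mean 4-week change among continuers differs from the mean that all device subjects would have shown. Because SAP 12.2 measures change from baseline, the 4-week figure also carries each continuer's first-14-day change with it.

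Nothing in the plan would reveal this. There is no comparison of continuers with non-continuers, no sensitivity analysis and no defined 4-week analysis set. The result is meant for publication, so a reader of it could not tell a treatment effect over weeks 3 and 4 from a change in who is being measured.

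**Working it through.** **1. Figures in the plan.** None applies. The documents give no continuation rate, no SD for the pain scale and no statement of who is likelier to continue. The size below is an illustration, not a reproduction.

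**2. What the stated method does.** Ratings after Day 14 exist only for those who elect the extension (Protocol 9.3). Repeated-measures ANOVA on complete cases (SAP 12, 12.4) needs a rating at every time point analysed. Applied to a 4-week series, it keeps continuers and drops the rest.

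**3. What the conflicting statements do.** Placing all subjects in the ITT analysis (SAP 11.2, 12.6) creates no week-4 rating for a subject who declined. Carrying the last visit forward is not a commitment, and declining an optional extension is not clearly a missed visit. If it were used, a Day-14 or earlier rating would stand in as a week-4 rating. The use of any extension days (SAP 11.3) leaves open how partial extension data enter. The 4-week set is therefore undefined, and the one firm rule selects on continuation.

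**4. Size on the pain scale.** All inputs are assumptions; improvement is counted as positive.

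- SD of improvement: 2.0-2.5 points
- Uptake u: 50-70%
- Correlation c between willingness to continue and Day-14 improvement: +0.5 or -0.5
- Correlation r between Day-14 and 4-week improvement: 0.6-0.8

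Continuers' shift at Day 14 = c × φ(z)/u × SD, where z is the normal cut-off giving uptake u. The factor φ(z)/u is 0.798 at 50% uptake and 0.497 at 70%. The shift at 4 weeks is the Day-14 shift × r.

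| Case (c = 0.5) | Day-14 shift | 4-week shift |
|---|---|---|
| u = 70%, SD 2.0, r = 0.6 | 0.5 × 0.497 × 2.0 = 0.50 | 0.50 × 0.6 = 0.30 |
| u = 50%, SD 2.5, r = 0.8 | 0.5 × 0.798 × 2.5 = 1.00 | 1.00 × 0.8 = 0.80 |

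With c = -0.5 the same values apply with the sign reversed. At |c| = 0.3 the 4-week range is 0.18-0.48 points, and at |c| = 0.7 it is 0.42-1.12.

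**5. The same point for responders.** Assume a true response of 50%. The responder share among continuers is 0.5a/(0.5a + 0.5b), where a and b are the continuation rates of responders and non-responders.

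- a = 0.9, b = 0.3: 0.45/0.60 = 75%
- a = b: 50%
- a = 0.5, b = 0.9: 0.25/0.70 = 36%

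**6. Does starting again at Day 14 solve it?** Not by itself. The continuers' mean change from Day 14 contains an artefact equal to the Day-14 shift × (1 - r). That runs from 0.50 × 0.2 = 0.1 to 1.00 × 0.4 = 0.4 points. It is regression to the mean: a spurious worsening if c is positive and a spurious further gain if c is negative, with no true mean change in either case.

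**The case against.** Three objections deserve weight.

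*The direction is not known.* A reader might infer that satisfied responders will be over-represented and that the 4-week improvement will come out too large. That is plausible: continuing means 2 hours of brace wear daily (Protocol 9.3), which a subject who was not helped has less reason to accept. The opposite is also plausible. Eligibility takes in minor strains and sprains (Protocol 8.4); a subject whose pain has resolved may stop while one still in pain carries on. No passage favours either account. This objection stands in full, so the illustration runs in both directions.

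*No passage restricts the 4-week analysis to continuers.* A reader might infer that the SAP specifies a continuers-only analysis. It does not; that is the consequence of its complete-case rule, and the ITT and last-visit wording points elsewhere. The objection stands as to wording. It does not remove the problem, because no alternative is specified that would supply or properly model the absent ratings.

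*The consequence is small.* The extension is exploratory, no 4-week result appears in the documents, and none of them plans to set a 4-week mean in continuers beside a 2-week mean in all device subjects. This stands, and it limits the weight of the point.

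**Conclusion.** The concern holds as a minor one, confined to the exploratory result. The 4-week change from baseline depends on self-selected subjects, the plan's statements about whom to analyse and how to treat absent ratings conflict, and bias is possible in either direction. Under the stated assumptions it is about 0.3-0.8 points up or down. SD, uptake and both correlations are assumed, and with no relation between willingness and improvement the shift is zero.

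The documents do not support the stronger conclusion that the 4-week improvement will be overstated. The 2-week primary endpoint uses ratings collected before the extension and is unaffected.

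A separate limitation points the same way. SOC subjects who enter the extension may cross over to the device, so no concurrent SOC group at week 4 is assured. Handling the selection would not make the 4-week result a controlled comparison.

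**What to change.** 1. **SAP 12.2 and 12.4:** estimate any 4-week device mean with a mixed model that includes the Day 0-14 ratings of all device subjects plus the extension ratings that exist. Let this replace complete-case ANOVA and last-visit imputation for this endpoint, and state the analysis set. The model corrects for selection that depends on the recorded ratings, as in the illustration. It does not correct for reasons to continue that those ratings do not capture, and the SAP should say so.
2. **One table:** Day-14 change for continuers and non-continuers, by original arm. This would show the direction of any selection on Day-14 improvement.
3. **Label:** describe the 4-week result as self-selected and uncontrolled wherever it is reported.
4. **Optional:** if change from Day 14 in continuers is also shown, present it as descriptive and note that regression to the mean affects it.

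The data are already scheduled for collection (Protocol 9.5, Table 1). The cost is SAP wording, slightly more analysis work and one table. The 4-week figure may turn out less favourable than a complete-case mean.
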